4.6.1 Extent of Exposure

Extent of exposure to both study treatments will be summarized. The duration of exposure will be presented in days and calculated as the date of last dose of study drug minus the date of first dose of study drug, plus one. Duration of exposure and total dose received (mg) will be summarized using descriptive statistics.

4.6.2 Adverse Events

Treatment-emergent adverse events (TEAEs) are defined as those AEs with onset after the first dose of study drug or existing events that worsened after the first dose during the study. Treatment-emergent AEs will be summarized by cohort and over all patients combined.

Specific to Cohort 3a, for patients who cross over to receive combination therapy, events that occur during the monotherapy period will be counted in the Cohort 3a monotherapy subcohort only. Events that occur after the end of monotherapy but prior to the first date of treatment within the combination period will also be counted in the Cohort 3a monotherapy subcohort only. Events occurring after the start of combination therapy will be counted in the Cohort 3a crossover subcohort only.

Events reported with a partial onset date (e.g., month and year are reported but the day is missing) will be considered to be treatment-emergent if it cannot be confirmed that the event onset was prior to the first dose of study drug based on the available date entries.

Verbatim terms on case report forms will be mapped to preferred terms and system organ classes using MedDRA, version 26.0.

Summaries that are displayed by system organ class and preferred terms will be ordered by descending incidence of system organ class and preferred term within each system organ class. Summaries displayed by preferred term only will be ordered by descending incidence of preferred term. Summaries of the following types will be presented:

- Overall summary of number of unique TEAEs and patient incidence of TEAEs meeting various criteria;
- Overall summary of number of unique treatment-emergent serious adverse events (SAEs) and patient incidence of treatment-emergent SAEs meeting various criteria;
- Patient incidence of TEAEs by MedDRA system organ class and preferred term;
- Patient incidence of the most frequently occurring TEAEs (i.e., TEAEs occurring in ≥ 10% of the Safety Analysis Set) by MedDRA preferred term;

- Patient incidence of TEAEs by CTCAE grade, MedDRA system organ class and preferred term;
- Patient incidence of TEAEs by relationship to nanatinostat, MedDRA system organ class and preferred term;
- Patient incidence of TEAEs by relationship to valganciclovir, MedDRA system organ class and preferred term;
- Patient incidence of TEAEs related to nanatinostat by CTCAE grade, MedDRA system organ class and preferred term;
- Patient incidence of TEAEs related to valganciclovir by CTCAE grade, MedDRA system organ class and preferred term;
- Patient incidence of TEAEs related to nanatinostat or valganciclovir by CTCAE grade, MedDRA system organ class and preferred term;
- Patient incidence of the most frequently occurring TEAEs related to nanatinostat (i.e., related TEAEs occurring in ≥ 10% of the Safety Analysis Set) by MedDRA preferred term;
- Patient incidence of the most frequently occurring TEAEs related to valganciclovir (i.e., related TEAEs occurring in ≥ 10% of the Safety Analysis Set) by MedDRA preferred term;
- Patient incidence of the most frequently occurring TEAEs related to nanatinostat or valganciclovir (i.e., related TEAEs occurring in ≥ 10% of the Safety Analysis Set) by MedDRA preferred term;
- Patient incidence of TEAEs leading to dose interruption of nanatinostat by MedDRA system organ class and preferred term;
- Patient incidence of TEAEs leading to dose interruption of valganciclovir by MedDRA system organ class and preferred term;
- Patient incidence of TEAEs leading to dose interruption of nanatinostat or valganciclovir by MedDRA system organ class and preferred term;
- Patient incidence of TEAEs leading to dose reduction of nanatinostat by MedDRA system organ class and preferred term;
- Patient incidence of TEAEs leading to dose reduction of valganciclovir by MedDRA system organ class and preferred term;
- Patient incidence of TEAEs leading to dose reduction of nanatinostat or valganciclovir by MedDRA system organ class and preferred term;
- Patient incidence of TEAEs related to nanatinostat leading to discontinuation of study drug by MedDRA system organ class and preferred term;

- Patient incidence of TEAEs related to valganciclovir leading to discontinuation of study drug by MedDRA system organ class and preferred term;
- Patient incidence of TEAEs related to nanatinostat or valganciclovir leading to discontinuation of study drug by MedDRA system organ class and preferred term;
- Patient incidence of SAEs by MedDRA system organ class and preferred term;
- Patient incidence of SAEs by CTCAE grade, MedDRA system organ class and preferred term;
- Patient incidence of SARs (nanatinostat) by MedDRA system organ class and preferred term;
- Patient incidence of SARs (valganciclovir) by MedDRA system organ class and preferred term;
- Patient incidence of SARs (nanatinostat or valganciclovir) by MedDRA system organ class and preferred term;
- Patient incidence of TEAEs leading to death by MedDRA system organ class and preferred term.

Select AE summaries will also be repeated for different age subgroups (<65 years old, ≥65 years old). Separate AE summaries may also be repeated for adolescents 12-17 years old if there are at least 5 patients enrolled for this age group. Selected AE summaries may be repeated in terms of exposure-adjusted rates in 100 patient-years.

At each level of summarization (e.g., any AE, system organ class, and preferred term), patients experiencing more than one TEAE will be counted only once. In the summary of TEAEs by CTCAE grade, patients will be counted once at the highest severity reported at each level of summarization; in the summary of TEAEs by relationship, patients will be counted once at the closest relationship to study drug. Related events include those reported as "Possibly Related" or "Definitely Related" to study drug; events considered not related are those reported as "Unrelated" to study drug.

For summaries of treatment-related TEAEs by CTCAE grade, a column summarizing patients with at least one treatment-related Grade \geq 3 TEAE will also be presented.

Adverse event data will be presented in data listings by patient, cohort, and event. Serious AEs and AEs leading to permanent discontinuation of the study drugs will also be presented in separate data listings.

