#### 3.1.3. Safety Follow-up Period

Upon discontinuation of the protocol-specified treatments, patients will enter the Follow-up period. All patients will be followed for AEs for 28 days after the last dose of study drug (permanent discontinuation) and complete the Safety Follow-up visit as described in Section 7.2.5, except if the patient is lost to follow-up or withdraws consent (see Section 8.1).

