## 7.2.5. Safety Follow-up Visit

The Safety Follow-up visit will occur approximately 28 days following the final administration of nanatinostat/valganciclovir. The Safety Follow-up visit has an allowable  $\pm 3$ -day window.

If a patient withdraws consent after the EOT visit but prior to the 28-day safety evaluation, safety data should be collected on the patient up to the date of consent withdrawal.

Adverse events will be assessed (contact by phone is permitted) until 28 days following the last dose of study drug. In addition to AEs, all concomitant medications given to a patient as a result of an AE during this period will be recorded on the Prior and Concomitant medication eCRF page. All new anti-lymphoma therapies given to a patient within 28 days after the last dose of study drug must be recorded in the eCRF.

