#### 7.3.2. Safety and Tolerability Assessments

Adverse events will be assessed, and concomitant medications, procedures, and hospitalizations will be recorded from the signing of the ICF until 28 days post-last dose of study treatment.

All 12-lead ECGs will be conducted in triplicate. Average corrected QT interval using Fridericia's method (QTcF) is to be calculated to confirm eligibility. For patients enrolled in any Stage 1 cohort, ECGs will be performed in triplicate, as described in Section 7.3.2.8. ECG tracings will be provided to a central laboratory, instructions are provided in the ECG Manual.

Viral levels [EBV, CMV, HHV-6, HHV-8, and HIV (for HIV+ patients only)] will be monitored for viral reactivation.

Tolerability will be assessed by the incidence of AEs leading to dose modifications or study drug discontinuation.

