#### 8. ADDITIONAL SAFETY CONSIDERATIONS

## 8.1. Monitoring, Recording and Reporting of Adverse Events

An AE is any untoward medical event that occurs to a patient following the start of administration of the study drugs, whether or not considered study drug related. An AE can, therefore, be any unfavorable and unintended sign (e.g., an abnormal laboratory finding), symptom or disease temporally associated with the use of a drug, whether or not considered related to the drug. For example, it may be a new intercurrent illness, a worsening concomitant illness, an injury, or any concomitant impairment of the patient's health, including laboratory test values (as specified by the criteria below), regardless of etiology. Any worsening (ie, any clinically significant adverse change in the frequency or intensity of a pre-existing condition) should be considered an AE. A diagnosis or syndrome should be recorded on the Adverse Events eCRF rather than the individual signs or symptoms of the diagnosis or syndrome.

An overdose, accidental or intentional, associated with an AE, or abuse, withdrawal, sensitivity, or toxicity to an investigational product should be reported as an AE. Overdoses with or without an associated AE will be recorded on the dosing eCRF. All patients will be monitored for AEs during the study and continue until 28 days after the last dose of study drugs or until a new anticancer treatment is started, whichever occurs first.

If the Investigator becomes aware of an SAE after the study-specified safety follow-up period and considers the event related to study drug, the event will be reported within 24 hours according to the procedures detailed in Section 8.2.1.

Assessments may include monitoring any or all of the following parameters: the patient's clinical symptoms, laboratory, pathological, radiological, or surgical findings, physical examination findings, or other appropriate tests and procedures.

All AEs will be recorded by the Investigator from the time the patient signs the informed consent. Adverse events and serious adverse events (SAE) will be recorded on the Adverse Events eCRF and in the patient's source documents. All SAEs must be reported to ICON Drug Safety within 24 hours of the Investigator's knowledge of the event by facsimile, or other appropriate method, using the SAE Report Form, or approved equivalent form.

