#### Clarification in Reporting of Deaths

Fatal events regardless of causality will be reported within 24 hours of the Investigator's knowledge through the safety follow period or until a new anticancer treatment is started,

whichever is first. Death is an outcome of an adverse event and not an adverse event in and of itself. All reports of death should include an adverse event term for the cause of death (if known).

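### Two adverse-event collection rules conflict when new anticancer therapy starts within 28 days of last dose, and the SAP's open-ended TEAE definition does not settle which events count

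*SAP*

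**What the plan says.** Four places set a plain 28-day window. Protocol 3.1.3 and SAP 3.1 follow every patient for adverse events for 28 days after permanent discontinuation. Protocol 7.2.5 says "Adverse events will be assessed (contact by phone is permitted) until 28 days following the last dose of study drug". Protocol 7.3.2 has adverse events assessed, and medications, procedures and hospitalizations that "will be recorded from the signing of the ICF until 28 days post-last dose of study treatment". None of the four names new therapy as a stopping point.

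Protocol 8.1 is different. Monitoring there is to "continue until 28 days after the last dose of study drugs or until a new anticancer treatment is started, whichever occurs first". Its clarification on deaths has fatal events reported "through the safety follow period or until a new anticancer treatment is started", whichever is first. Protocol 8.6 applies the same earlier-of rule to what is recorded. SAP 3.4.2.1 repeats the Protocol 8.1 sentence but breaks off before the word *first*. The SAP therefore contains both rules.

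Protocol 8.1 also extends reporting: "If the Investigator becomes aware of an SAE after the study-specified safety follow-up period and considers the event related to study drug", the event is still to be reported within 24 hours. No end date is given.

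The only TEAE definition is in SAP 4.6.2: "those AEs with onset after the first dose of study drug or existing events that worsened after the first dose during the study". The protocol makes TEAE incidence and severity a secondary endpoint without defining the term.

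**The concern.** A patient who stops for progression may begin salvage chemotherapy within days. A site that follows Protocol 7.2.5 would record a cytopenia caused by that chemotherapy, whereas a site that follows 8.1 or 8.6 would not. Once recorded, the event meets the SAP definition and is tabulated as treatment-emergent for nanatinostat and valganciclovir.

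The overlap in toxicity is real. In the earlier study of the combination, Protocol 1.2.4 lists neutropenia, thrombocytopenia and anemia as the most frequent Grade 3/4 events, and cytotoxic salvage treatment also causes these. At stake is the meaning of a secondary safety endpoint, which would depend partly on the section a site followed. The cut-off might also end up being chosen after the data are seen, and SAP section 1 says its purpose is to avoid post hoc decisions.

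**Working it through.** The plan gives no figure to reproduce, so the check sets the texts side by side.

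**Step 1. Where each passage ends the window**

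| Place | End of window | Stops at new therapy? |
|---|---|---|
| Protocol 3.1.3 | 28 days after last dose | No |
| Protocol 7.2.5 | 28 days after last dose | No |
| Protocol 7.3.2 | 28 days after last dose | No |
| SAP 3.1 | 28 days after last dose | No |
| Protocol 8.1 | Earlier of 28 days and new therapy | Yes |
| Protocol 8.1, deaths | Earlier of safety follow-up end and new therapy | Yes |
| Protocol 8.6 | Earlier of 28 days and new therapy | Yes |
| SAP 3.4.2.1 | 28 days or new therapy, order not stated | Unclear |
| SAP 4.6.2, TEAE | None | No |

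**Step 2. Who is affected, and for how long.** Let d be the days from last dose to new anticancer therapy. The first rule ends at day 28 and the second at min(28, d). The difference is max(0, 28 − d). For illustrative values of d, which are assumptions:
- d = 7: 28 − 7 = 21 days
- d = 14: 28 − 14 = 14 days
- d = 21: 28 − 21 = 7 days
- d = 28 or more: 0 days

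Protocol 7.2.5 expects d below 28 in some patients: "All new anti-lymphoma therapies given to a patient within 28 days after the last dose of study drug must be recorded in the eCRF". Neither document says how often.

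**Step 3. Whether an event in the disputed days is a TEAE.** Its onset is after first dose and the patient is still in follow-up, so it qualifies. For patients who do not complete the study, SAP 4.6 takes all data available up to study discontinuation, not treatment discontinuation, so it imposes no cut either. The omission looks unintended, because SAP 4.6.5.6 ends the concomitant-medication window 28 days after last dose and SAP 4.6.2 sets cut points for Cohort 3a crossover.

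**Step 4. Which tables are exposed.** The all-cause TEAE, serious-event, worst-grade and TEAE-leading-to-death tables take the event whatever its cause. The related-event tables depend on the investigator's judgment. Under Protocol 8.4, an event is unrelated only if its timing makes a causal link very unlikely and there is also another reasonable explanation. An event that fits neither extreme category is possibly related, and SAP 4.6.2 counts that as related. A cytopenia two weeks after last dose, following new chemotherapy, could fall there.

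**Step 5. How far the open end reaches.** Protocol Table 5 schedules adverse-event collection through the 28-day Safety Follow-up visit and none in long-term follow-up. Beyond day 28, the open definition mainly adds late serious events judged related, and the SAP does not say how these are to be counted.

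**The case against.** The strongest reply is that the dedicated sections govern. Protocol 8.1 and 8.6 agree, 8.6 says outright what is recorded, and a specific reporting section normally overrides a visit overview. Protocol 3.1.3 ends with a pointer to Section 8.1. In 7.3.2, the verb for recording attaches grammatically to medications, procedures and hospitalizations, while adverse events are only assessed.

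Part of this stands. Section 7.3.2 is the weakest of the four uncapped passages. The pointer in 3.1.3, however, reads most naturally as belonging to the exception for loss to follow-up or withdrawn consent. Section 7.2.5 states the uncapped rule in the same section that foresees new therapy inside the 28 days. Even if 8.1 and 8.6 govern, nothing in SAP 4.6.2 removes an event that a site did record.

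It can also be said that the effect is small. SAP 4.6.2 counts a patient once at each level of summarization, at the highest grade in the grade tables, so a patient who already had neutropenia on study drug adds nothing unless a new term or a higher grade appears. Eligibility requires that no standard therapy be available, and some patients may continue study drug past progression, which makes rapid next therapy less certain. The analysis is descriptive, with no cohort comparison. These points limit the size of the problem, but the contradiction remains.

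**Conclusion.** The point holds within narrow limits. The collection passages conflict for patients who start new anticancer therapy within 28 days of last dose, for at most 28 days each, and the SAP's TEAE definition does not resolve the conflict. The all-cause tables are exposed, and the related-event tables are partly protected. The primary endpoint and the stage decisions are untouched. This should be corrected, but it does not threaten the trial's main conclusion.

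A reader might infer two stronger claims that the documents do not support. One is that the missing end date brings years of later toxicity into the tables; Protocol Table 5 ends routine collection at the 28-day visit. The other is that a known share of patients, or a known inflation of TEAE rates, follows. The documents give no time to next therapy, and a count of patients with a disputed window would not be a count of miscounted events. The size of the effect is therefore unknown.

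The conclusion assumes only that some patients start new therapy inside the window and that sites may differ in which section they follow.

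**What to change.** Reconcile Protocol 3.1.3, 7.2.5, 7.3.2, 8.1 and 8.6 and SAP 3.1 and 3.4.2.1 to one collection rule, and restore *first* in SAP 3.4.2.1.

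In SAP 4.6.2, define a TEAE as onset or worsening from first dose through the earlier of 28 days after last dose and the day before the first new anticancer therapy, plus any later recorded adverse event, serious or not, judged related to study drug. Keeping non-serious related events matters; otherwise a delayed related cytopenia that begins after the next therapy would leave the tables. State that Cohort 3a crossover to the combination is not new anticancer therapy. Apply the cut by program to all patients, whatever a site recorded, and list the excluded events.

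The earlier-of window is preferable to a plain 28-day window because events that a site never recorded after new therapy cannot be recovered, whereas the shorter window can be applied to everyone. The therapy dates are already to be collected under Protocol 3.1.2 and 7.2.5.

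The cost is a short SAP revision and aligned protocol wording. The downside is that some unrelated events within 28 days of last dose, but after new therapy, move from tables to a listing.

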## 9.7. Safety Analysis

Safety analysis will be based on all patients in the Safety population and will be summarized overall, by cohort, and by any other relevant subgroup, such as randomization to monotherapy.

Study medication exposure will be summarized for each patient and tabulated by cohort including duration of study medication, total dose taken, and dose reductions.

Adverse events, vital sign measurements, clinical laboratory measurements, and concomitant medications will be summarized overall and by cohort. Tabulations and listings of values for vital signs and laboratory safety evaluations will be presented.

Adverse events will be coded according to MedDRA and classified using the NCI CTCAE Version 5.0. The incidence rates of AEs will be tabulated by System Organ Class and Preferred Term. Subsets of AEs to be summarized include serious AEs (SAEs), events of all CTCAE grade severities, suspected treatment-related AEs, and events that resulted in withdrawal of study medication. The most severe grade of each preferred term for a patient will be utilized for summaries of AEs by NCI CTCAE grade. All AEs with corresponding attributes will be displayed in a by-patient listing. Adverse events leading to death or to discontinuation from treatment, events classified as NCI CTCAE Grade 3 or higher, suspected treatment-related events, all deaths, and SAEs will also be displayed in by-patient listings separately.

Clinical laboratory results will be summarized descriptively by cohort, which will also include a display of change from baseline. Laboratory values outside of the normal ranges will be identified. Clinically significant hematologic and non-hematologic laboratory abnormalities that meet Grade 3 or Grade 4 criteria according to the CTCAE will be listed and summarized. Graphical display of selected lab parameters over the course of study will be provided.

Vital sign measurements will be listed for each patient at each visit. Descriptive statistics for vital signs, both observed values and changes from baseline, will be summarized by cohort.

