The method of assigning patients to individual cohorts is described in detail in Section 3.3.2. It is estimated that up to 486 patients in Cohorts 1 to 6 may be enrolled for combination therapy, of which approximately 60 would be enrolled in Stage 1 and 66 would be enrolled in Stage 2, and up to 360 would be enrolled into the post-Stage 2 expansion cohorts. Additional patients (n=10) with PTCL will be enrolled in Cohort 3a for nanatinostat monotherapy, and patients with lymphoma subtypes other than those assigned to Cohorts 1, 3, 4, 5, and 6 may be enrolled into Cohort 7 (with the exception of France).

If 10 patients of a given lymphoma subtype are enrolled into Cohort 7, then the Simon's decision criteria will be applied to determine whether or not to add patients in Stage 2 for that subtype. If none of the subtypes represented in Cohort 7 enrolls at least 10 patients, efficacy data collected on those patients will be listed but not summarized by group.

Enrolled patients will receive treatment until disease progression (per Investigator assessment), unacceptable toxicity, withdrawal of consent, Investigator's discretion, death, initiation of new antineoplastic therapy, discontinuation from the study for any

reason, or study termination by the Sponsor. All antineoplastic therapies given after the last dose of study drug (and time to next therapy) will be recorded in the electronic case report form (eCRF) (unless the patient withdraws consent or is lost to follow-up). Patients will be followed for survival regardless of treatment discontinuation reason (except if consent is withdrawn or patient is lost to follow-up).

Study treatment will start on Cycle 1 Day 1. Patients enrolled in Cohorts 1 to 7 (with the exception of Cohort 3a), and patients crossed over from Cohort 3a will receive intermittent dosing of nanatinostat and continuous valganciclovir in 28-day cycles. Nanatinostat and valganciclovir will be taken at the same time following a light meal. During treatment Cycle 1, visits will occur on Days 1, 8, 15, and 22. Starting at Cycle 2, visits will occur on Days 1 and 15. Each scheduled clinic visit has an allowable ±3-day window.

For Cohort 3a, the PTCL patients randomized to monotherapy will begin with 6 weeks of nanatinostat monotherapy (20 mg orally once daily on Days 1 to 4 per week) with visits on Days 1, 15, 29, and 43. Each scheduled clinic visit has an allowable ± 3 -day window.

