3.3.2 Method of Assigning Patients to Cohorts

Patients will be enrolled utilizing Simon's 2-stage design options for discontinuing enrollment into each cohort where treatment appears to be futile. In Stage 1, 6 cohorts (Cohorts 1, 2, 3b, 4, 5, and 6) will enroll up to 10 patients each. Patients will be enrolled into each cohort based on their primary lymphoma diagnosis to receive the combination nanatinostat plus valganciclovir with exception of Cohort 3a.

The first 20 patients enrolled with PTCL in Cohort 3 will be randomized 1:1 to either Cohort 3a (nanatinostat monotherapy) or Cohort 3b (nanatinostat plus valganciclovir). Randomization will occur at the time of drug dispensation for Cycle 1 Day 1. Following a disease response assessment at 6 weeks, patients in Cohort 3a with a CR or PR will continue nanatinostat monotherapy. Those in Cohort 3a with stable disease at 6 weeks or disease progression at any time will be offered the option to cross over to receive combination therapy for the remainder of the study, provided they qualify per hematology, chemistry, no sign of CNS disease progression, and ECOG performance status parameters.

All cohorts that have a response in 2 or more patients in Stage 1 will expand enrollment by 11 patients in Stage 2, for a total of 21 patients in each cohort (Figure 2). If \geq 7 responses are observed in the initial 21 patients in any cohort, then enrollment will be expanded to include up to 120 additional patients in that cohort (N=141), with an interim analysis of efficacy and safety planned in the second-line EBV⁺ lymphoma

subpopulation (see Section 4.7 for sample size details). Data from a total of 40 patients who have been followed for at least 6 months or permanently discontinued study treatment will be used for this interim analysis. If the interim efficacy analysis outcome is positive (see Section 4.5.6.3 for details of this interim efficacy analysis), then the final analysis would still be conducted for all second-line EBV⁺ lymphoma patients and the entire cohort. Cohort 3a will not enroll beyond the initial 10 patients, regardless of the number of responders in Stage 1. See Section 4.7 for details.

Cohort 7 will be closed to enrollment when all other cohorts are closed, or sooner at the discretion of the Sponsor, regardless of the number of patients recruited at that time and will not be subject to the decision criteria of the Simon's 2-stage design.

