4.6 Safety Evaluation

Safety analysis will be carried out for the Safety Analysis Set as defined in Section 4.2 to include all patients who receive at least one dose of study drug. Patients who do not complete the study, for whatever reason, will have all available data up until the time of study discontinuation included in the safety analysis.

For the Simon 2-stage part of the study, since Cohort 3 (PTCL) patients are initially randomized to monotherapy or combination therapy, their data will be summarized as follows for occurrence-based analyses: patients randomized to monotherapy, patients who start on monotherapy and then cross over to combination therapy, and patients randomized to combination therapy. For analyses presented by study visit, their data will be summarized as randomized.

In addition, all patients who receive combination therapy at any point on study (to include Cohort 3a patients who cross over from monotherapy to combination therapy

during the Simon 2-stage part of the study) will be summarized across both parts of the study separately by cohort and also overall.

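### Crude adverse-event percentages for Cohort 3a monotherapy and randomized Cohort 3b cover different time windows, and no committed table makes them comparable

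*SAP*

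**What the plan says.** SAP 3.3.2 sets up the randomized pair: "The first 20 patients enrolled with PTCL in Cohort 3 will be randomized 1:1", which gives 10 patients in 3a (nanatinostat alone) and 10 in 3b (the combination). SAP 3.1 states that "the PTCL patients randomized to monotherapy will begin with 6 weeks of nanatinostat monotherapy". What follows depends on response:

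- "patients in Cohort 3a with a CR or PR will continue nanatinostat monotherapy", with no set end.
- "Those in Cohort 3a with stable disease at 6 weeks or disease progression at any time will be offered the option to cross over".

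Protocol Table 6 (footnote 1) requires the switch within 7 days of the disease assessment. Cohort 3b patients are treated until progression, toxicity or another stop. Adverse events are followed for 28 days after the last dose, or until new anticancer treatment if that comes first (SAP 3.1; Protocol 8.1).

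For occurrence-based safety tables, SAP 4.6 names three groups: "patients randomized to monotherapy, patients who start on monotherapy and then cross over to combination therapy, and patients randomized to combination therapy". Protocol 9.7 likewise asks for safety summaries "by cohort, and by any other relevant subgroup, such as randomization to monotherapy". Under SAP 4.6.2, events up to the first combination dose belong to the monotherapy group. After that, "Events occurring after the start of combination therapy will be counted in the Cohort 3a crossover subcohort only".

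The tables listed in SAP 4.6.2 are patient incidence, with event counts added in the two overall summaries. Exposure adjustment is left open: "Selected AE summaries may be repeated in terms of exposure-adjusted rates in 100 patient-years".

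**The concern.** A crude percentage answers how many patients had the event while they were being watched. If one group is watched for about 6 weeks and the other for several months, the percentages differ even when the underlying event rates are identical.

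This pair is the study's only randomized view of what adding valganciclovir does to tolerability. Protocol section 3 says there are no clinical monotherapy data with nanatinostat in lymphoma patients. Protocol 1.3.2 names thrombocytopenia and renal dysfunction as overlapping toxicities that may be more frequent or more severe in combination. A window effect would usually push in the same direction as that expected real effect, and full-period crude columns cannot separate the two.

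**Working it through.** The documents state no incidence figure for this contrast, so there is no plan figure to reproduce. The calculations below are illustrations under stated assumptions.

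**Step 1. The windows.**

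| Group | Window for the crude column |
|---|---|
| 3a, crosses over | First dose to first combination dose: about 6 to 7 weeks nominally, less after early progression |
| 3a, responds | Monotherapy continues, no set end |
| 3b | First dose to last dose, plus up to 28 days |

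**Step 2. Same constant hazard in both groups.** Assume 0.10 events per 4 weeks. Incidence by week *w* is 1 − exp(−0.10 × *w*/4).

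- 6 weeks (3a crossover): 1 − exp(−0.15) = 13.9%
- 12 weeks (3b, 8 weeks of treatment plus 4): 1 − exp(−0.30) = 25.9%
- 28 weeks (3b, 24 weeks of treatment plus 4): 1 − exp(−0.70) = 50.3%

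**Step 3. Let 3a responders stay on and 3b patients progress early.** Assume the same hazard in both groups with a 20% six-week risk, so incidence by week *w* is f(*w*) = 1 − 0.8^(*w*/6). Then f(6) = 20.0%, f(12) = 36.0% and f(28) = 64.7%. All 3a non-responders are taken to cross over at week 6. 3a responders are followed to week 28 (24 + 4).

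In 3b, a share progresses at the week-8 scan and is followed to week 12; the rest are followed to week 28. The assumed progression share is 50% or 30%.

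- 3b, 50% progress: 0.5 × 36.0 + 0.5 × 64.7 = 50.4%
- 3b, 30% progress: 0.3 × 36.0 + 0.7 × 64.7 = 56.1%

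| 3a responder share | 3a monotherapy | 3b |
|---|---|---|
| 10% | 0.90 × 20.0 + 0.10 × 64.7 = 24.5% | 50.4% to 56.1% |
| 35% | 0.65 × 20.0 + 0.35 × 64.7 = 35.6% | 50.4% to 56.1% |
| 47% | 0.53 × 20.0 + 0.47 × 64.7 = 41.0% | 50.4% to 56.1% |

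The 10% and 35% shares are borrowed from the Simon design rates. The 47% is the upper end of the response range that Protocol 1.1.2 gives for other single agents. None is a known rate for nanatinostat alone.

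**Step 4. A common six-week window.** With equal hazards and a 20% six-week risk, both groups show 20%. If the combination hazard were truly 1.5 or 2 times higher, 3b would show 1 − 0.8^1.5 = 28.4% or 1 − 0.8^2 = 36.0% against 20%. The artefact goes and a real difference still shows.

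**Step 5. The optional exposure-adjusted rate.** SAP 4.6.1 defines exposure as last dose minus first dose plus one, with no split at crossover. Suppose a 3a patient has 6 weeks of monotherapy and then 16 weeks of combination (illustrative). Using that duration as person-time would divide 6 weeks of monotherapy events by 22 weeks and understate the monotherapy rate by 22/6 = 3.7-fold.

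**The case against.** The attribution rule itself is right: events after the first combination dose should not be charged to monotherapy. SAP 4.1.1 plans no formal comparison of cohorts, the safety objective is to describe the combination, and Cohort 3a exists mainly to look at single-agent activity. With 10 patients per group, 14% versus 26% is about 1.4 versus 2.6 patients.

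There is also mitigation. The toxicities of most interest are laboratory measures, which SAP 4.6.4 summarizes by visit, with creatinine and creatinine clearance plotted over time. SAP 4.6 presents by-visit data as randomized, so the crossover cut does not affect them. Exposure duration is tabulated, and adverse events are listed by patient.

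Most of this stands, and it limits the importance of the point. It does not remove it: SAP 4.6 itself names these groups for the occurrence-based tables, and with no test planned, those tables are what a reader will use.

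A reader might go further and infer that monotherapy will look safer only because most of its patients are watched for 6 weeks. The documents do not support that:

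- Protocol 1.3.2 reports 2- to 2.5-fold higher nanatinostat exposure with valganciclovir, so a real difference is expected.
- Crossover is optional, responders stay on monotherapy, and no monotherapy response rate is given. At a 47% response rate, the chance that at least 6 of 10 patients are non-responders is 0.453; at 10% it is 0.998.
- Events confined to the first weeks would show little or no window effect.

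**Conclusion.** The point holds as one of comparability. Full-period crude incidence for 3a monotherapy and for randomized 3b covers different observation times, and nothing that SAP 4.6.2 commits to corrects for this. Part of any observed difference may be due to time at risk, mixed with a real difference; the planned incidence tables cannot say how much.

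At equal hazards, the illustrations run from a wide gap (13.9% versus 50.3%) to a modest one (41.0% versus 50.4%). All rest on an assumed constant hazard and on assumed response, progression and treatment durations. The gap narrows with more 3a responders, earlier progression in 3b, or early-onset events. The documents do not support saying that the whole difference would be an artefact, or that monotherapy is bound to look safer. This is a worthwhile, low-cost improvement to descriptive tables; the study's primary conclusions are untouched.

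**What to change.** In SAP 4.6.2, for the randomized Cohort 3 patients:

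1. Add incidence of TEAEs, Grade 3 or higher TEAEs, SAEs and events leading to dose modification over Day 1 to Day 43 in both groups. Cut 3a patients at the first combination dose if it comes before Day 43. Keep 3b patients on the full Day 1 to Day 43 window. The cut must be worded for 3a only, because a 3b patient's first combination dose is on Day 1.
2. Footnote the full-period crude columns as not comparable between 3a monotherapy and 3b.
3. If exposure-adjusted rates are shown for Cohort 3, state that 3a monotherapy person-time ends at the first combination dose. Treat these rates as supportive: they assume a roughly constant hazard, and 10 patients followed for 6 weeks give only about 1.15 patient-years, so one event is about 87 per 100 patient-years.

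The cost is SAP wording and a few extra descriptive tables from onset and dosing dates already collected. No study procedure changes.
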